3.2 Exclusion Criteria

3.2.1 Patients who have received prior treatment for lymphoma are not eligible.

NOTE: Patients may have received corticosteroids for lymphoma for 10 or fewer days at any dose (no washout period required).

NOTE: Patients may have received up to 1 prior dose of rituximab before registration. In this case, patients will only receive 3 doses of rituximab on study, as specified in section 4 1.1.2.1.

3.2.2 Patients who have received chemotherapy (including monoclonal antibodies) or radiotherapy, administered for any condition, within 4 weeks prior to registration are not eligible.

NOTE: Patients may have received one dose of rituximab prior to enrollment. In such cases, patients will only continue with 3 doses of rituximab during induction (4 total doses).

3.2.3 Patients who have had prior surgical intervention for lymphoma, unless performed for the sake of tissue diagnosis or on an urgent basis for disease-related threat to life, limb, or organ function, are not eligible.

3.2.4 Patients with incomplete recovery from adverse events due to agents administered more than 4 weeks prior to registration are not eligible.

3.2.5 Patients must not have ongoing treatment with any other investigational agents ≤ 14 days prior to registration.

3.2.6 Patients must not have known CNS involvement of lymphoma.

3.2.7 Patients must not have a history of allergic reactions attributed to compounds of similar chemical or biologic composition to brentuximab vedotin and/or rituximab.

3.2.8 Patients must not have an uncontrolled intercurrent illness including, but not limited to, ongoing or active infection, symptomatic congestive heart failure, unstable angina pectoris, cardiac arrhythmia, or psychiatric illness/social situations that would limit compliance with study requirements.

3.2.9 Patients must not have known HIV infection.

3.2.10 Patients must not have known JC virus infection and/or progressive multifocal leukoencephalopathy (PML).

3.2.11 Patients are not eligible who have clinically active hepatitis B (tested at screening) or known hepatitis A or C infections.

NOTE: Patients with chronic HCV or HBV infection may enroll if other laboratory criteria are met. Those with HBV surface antigen positivity may enroll only if maintained on appropriate suppressive antiviral therapy, per treating investigator's discretion, for the duration of enrollment in the trial.

3.2.12 Pregnancy or active nursing of an infant is not permitted.

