4.3 Toxicities and Dosing Delays/Dose Modifications

All patients receiving at least one treatment on this protocol will be evaluable for toxicity. Each patient will be assessed for the development of toxicity according to the Time and Events Table (See Section 6.4). Toxicity will be assessed according to the CTCAE v 4.03, and pre-dose lab values must be assessed prior to dosing at each treatment visit. Dose adjustments should be made according to the system showing the greatest degree of toxicity.

Treatment modifications and dosing delays are to follow in Tables 3 and 4 below. For the phase I component, those events constituting a DLT also warrant treatment/modification as outlined below. In the event that both study agents could be responsible for a given toxicity, the treating investigator should first modify only the dose of the most likely offending agent; brentuximab vedotin should be adjusted before that of rituximab, as most toxicities are more common with this agent. Study treatment should not be delayed but rather, skipped & not be made up. Cycles should not be extended, if possible. If the dose of brentuximab vedotin is skipped or decreased due to toxicity, the dose may be restarted or increased for that individual patient in the event that the toxicity resolves completely (at the treating investigator's discretion).

Please also refer to sections of this protocol that contain more detailed information on the potential adverse events and risks associated with each agent (Sections 1.2.1.1 and 1.2.2.1). Any patient missing more than 3 consecutive administrations due to toxicity must be removed from the study. Doses reduced per protocol due to occurrence of adverse events are not counted as missed doses.

TABLE 3a: Drug-Related Hematological Toxicity Dose Reductions for Brentuximab vedotin - ANC

ANC	Action
$\geq 1,500/\mu\text{L}$	None.

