50,000-74,000/ μL	
-1st Occurrence: Notify treating investigator. Withhold current dose until ANC $\geq 1,500/\mu\text{L}$ and platelets $\geq 100,000/\mu\text{L}$. Do not replace missed doses. Restart next treatment at 50% previous dose.
 
-2nd Occurrence: Withhold current dose until ANC $\geq 1,500/\mu\text{L}$ and platelets $\geq 100,000/\mu\text{L}$. Do not replace missed doses. Restart next treatment at 25% previous dose.
 
-3rd Occurrence: Discontinue protocol therapy.

<50,000/ μL	
-1st Occurrence: Withhold current dose until ANC $\geq 1,500/\mu\text{L}$ and platelets $\geq 100,000/\mu\text{L}$. Restart next treatment at 25% previous dose.
 
-2nd Occurrence: Discontinue protocol therapy.

TABLE 4 Drug-Related Non-Hematological Toxicity Dose Reductions for Brentuximab vedotin & Rituximab ¹

CTCAE v 4.03 Grade	Brentuximab vedotin	Rituximab
0-2	No change from original starting dose	No change from original starting dose
3-4	Skip treatment until resolved to \leq Grade 2, then reduce by 33%	May continue if toxicity is clinically attributed to brentuximab vedotin. Otherwise, skip treatment until resolved to \leq Grade 2, then resume at same dose
Second episode of grade 3 or 4 toxicity	Skip treatment until resolved to \leq Grade 2, then reduce by 33%	May continue if toxicity is clinically attributed to brentuximab vedotin. Otherwise, skip treatment until resolved to \leq Grade 2, then resume at same dose
Third episode of grade 3 or 4 toxicity	Remove subject from trial	Remove subject from trial

¹ This table should be followed for all non-hematological toxicities EXCEPT peripheral neuropathy, hyperamylasemia, and pancreatitis, which should be managed as outlined below. In cases involving hyperbilirubinemia that is primarily indirect, and considered not reflective of underlying liver disease (ie, resulting from transfusion of red blood cells), treating investigators may consider avoiding protocol-specified dose reductions, after consultation with principal investigator.

Management of peripheral neuropathy:

- For new or worsening Grade 2 or 3 peripheral neuropathy, brentuximab vedotin should be withheld until neuropathy improves to Grade 1 or baseline and then restarted at a dose of 1.2 mg/kg. Missed doses will not be made up.
- For grade 4 peripheral neuropathy, discontinue treatment with brentuximab vedotin.

Dose modifications regarding hyperamylasemia and pancreatitis

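### Table 4 has no stop for PML, anaphylaxis or SJS/TEN: its default after a first or second resolved Grade 3–4 event is to resume both drugs

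*Combined protocol and SAP*

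**What the plan says.** Table 4 (section 4.3) covers drug-related non-hematological toxicity. Footnote 1 fixes its scope: "This table should be followed for all non-hematological toxicities EXCEPT peripheral neuropathy, hyperamylasemia, and pancreatitis, which should be managed as outlined below". A separate sentence allows discretion for indirect hyperbilirubinemia.

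For a first Grade 3–4 episode, and again for a second, brentuximab is skipped until Grade 2 or lower, "then reduce by 33" percent. For rituximab the table says "May continue if toxicity is clinically attributed to brentuximab vedotin". Otherwise rituximab is skipped until Grade 2 or lower, "then resume at same dose". The table requires removal only at a third episode.

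The text above the tables deals with toxicity that either drug could have caused: "the treating investigator should first modify only the dose of the most likely offending agent; brentuximab vedotin should be adjusted before that of rituximab". The stated reason is that most toxicities are more common with brentuximab.

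Two kinds of event have their own stops. One line reads "For grade 4 peripheral neuropathy, discontinue treatment with brentuximab vedotin". Severe pancreatitis, or a second mild-to-moderate episode, ends brentuximab permanently.

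At entry, 3.2.7 says "Patients must not have a history of allergic reactions attributed to compounds of similar chemical or biologic composition to brentuximab vedotin and/or rituximab", and 3.2.10 excludes patients with known JC virus infection or PML.

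**The concern.** The protocol names these events as risks. Section 1.2.1.1 reports two anaphylaxis cases in phase 1 trials of brentuximab. It also reports one case each of PML and SJS in the two phase 2 trials (160 patients), regardless of causality. Section 8.1.10 lists PML, SJS and TEN for brentuximab, and 1.2.2.1 lists PML for rituximab.

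Because footnote 1 excepts none of them, they get the same default as any other Grade 3–4 non-hematological toxicity: wait for Grade 2 or lower, then resume. For PML, and for allergy to similar compounds, the protocol would not have let the patient start. At stake is re-exposure after an event of this kind because the dosing table, read literally, points that way. The patients are already immunosuppressed and are treated at more than one site.

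**Working it through.** This is a check of text. The plan gives no figure to reproduce, so the provisions are set side by side.

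1. **Scope.** Footnote 1 excepts three categories. PML, anaphylaxis and SJS/TEN are not among them, so drug-related cases fall under Table 4.

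2. **Event-specific stops elsewhere.** None was found. Sections 1.2.1.1, 1.2.2.1 and 8.1.10 describe risks without dosing instructions. Sections 3.2.7 and 3.2.10 govern entry only. Section 4.1.6.1.2 says to interrupt or slow rituximab for infusion reactions and continue at half the rate on improvement; it has no line for anaphylaxis.

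3. **Provisions that can stop treatment.**
   - 4.6.3 and 4.6.5: unacceptable adverse events, or the investigator's judgment of the patient's condition.
   - 4.8, items 5.5.5 and 5.5.6: unsafe toxicity, or the physician's judgment. Withdrawal for safety is possible at any time.
   - 4.3, brentuximab restart: at the investigator's discretion, and worded for toxicity that has resolved completely.
   - 4.3, missed doses: removal is mandatory after more than 3 consecutive missed administrations due to toxicity.

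4. **What the missed-dose rule reaches.** Assume misses are counted per drug. In maintenance, the fourth consecutive missed brentuximab dose falls 3 × 3 = 9 weeks after the first missed one, and the fourth missed rituximab dose 3 × 6 = 18 weeks after. The rule therefore catches an event that stays above Grade 2, which is plausible for PML. It does not catch one that resolves before four doses are missed, or rituximab that was never skipped.

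5. **Rituximab in suspected PML.** The one-agent-first sentence points to changing brentuximab and leaving rituximab for later. Table 4 points to skipping rituximab unless the event is attributed to brentuximab. PML is listed for both drugs, so the action depends on an attribution that may not be possible at the bedside.

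6. **What resuming means in dose.** These figures apply to any Grade 3–4 event under Table 4 and only illustrate the rule. The table does not say which dose the second 33% is taken from, so two readings are shown.

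| Episode | Brentuximab from 1.2 mg/kg (induction, consolidation) | Brentuximab from 1.8 mg/kg (maintenance) | Rituximab |
|---|---|---|---|
| First | 1.2 × 0.67 = 0.804 | 1.8 × 0.67 = 1.206 | 375 mg/m² |
| Second, cut from the reduced dose | 1.2 × 0.67² = 0.539 | 1.8 × 0.67² = 0.808 | 375 mg/m² |
| Second, both cuts from the original dose | 1.2 × 0.34 = 0.408 | 1.8 × 0.34 = 0.612 | 375 mg/m² |

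**The case against.** The best defence is that Table 4 sets the dose while treatment continues, and 4.6 and 4.8 decide whether it continues. An investigator facing PML or anaphylaxis can stop at once, and most would. Section 11.6.1 also allows deviation to remove an immediate hazard. An event that does not resolve leads to compulsory removal. No passage says that permanent discontinuation is required for these events, and no harm is shown.

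Much of this stands, and it rules out several stronger readings that a reader might infer:

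- *The protocol compels re-treatment.* It does not. The general stops apply throughout, and restarting brentuximab is discretionary.
- *Stopping rests only on undefined terms such as unacceptable or unsafe.* It does not, because the missed-dose rule is mandatory and specific.
- *General stops and Table 4 conflict, with no order of precedence.* This makes too much of the point, because 4.6 and 4.8 limit any dosing.
- *Rituximab is left unmodified in any shared toxicity.* The text does not settle this. Table 4 skips rituximab unless the event is attributed to brentuximab.
- *Entry is stricter for all three events.* This is true of PML and of allergy to similar compounds. There is no entry exclusion for SJS/TEN.

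The defence does not supply a rule for an event that resolves quickly. There the only specific instruction is to resume. The protocol also did not leave neuropathy and pancreatitis to general judgment. Pancreatitis had a reported incidence of 0.27% in trials and compassionate use (1.2.1.1), and Amendment 1 gave it its own management rules for safety reasons (Appendix C).

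**Conclusion.** The point holds as a gap in a written safety rule. For a first or second drug-related Grade 3–4 PML, anaphylaxis or SJS/TEN event that settles to Grade 2 or lower, the default is to resume brentuximab at a 33% reduction and rituximab at full dose. Rituximab may go uninterrupted if the event is attributed to brentuximab.

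Support differs by event. For anaphylaxis, the general stops are discretionary and the missed-dose rule is unlikely to bite, on the assumption that the event resolves quickly; the documented cases are with brentuximab, while rituximab is listed for infusion reactions. For PML, the weakness is unclear direction on rituximab, alongside a stricter entry rule. For SJS/TEN, the case rests on its being a listed serious risk and on analogy with the existing neuropathy and pancreatitis stops.

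The size of any harm is unknown: the documents give no rate of resolution or re-dosing. This is a cheap improvement for patient safety. It does not affect the trial's efficacy inference and relies on no outside labelling.

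**What to change.** Add PML, anaphylaxis and SJS/TEN to the footnote 1 exceptions, with two lines below the table:

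- PML: hold both drugs while it is suspected and permanently discontinue both if it is confirmed, notwithstanding the one-agent-first sentence in 4.3.
- Anaphylaxis or SJS/TEN: permanently discontinue the causative drug.

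The sponsor's clinicians should confirm the wording. The cost is a short amendment to one footnote and two added lines. The downside is an occasional discontinuation earlier than an investigator would have chosen.

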Patients achieving **PD** at first re-staging should be taken off treatment and treated with R-CHOP or similar chemotherapy at the discretion of the local treating investigator.

Patients achieving **SD** should likewise be taken off treatment and treated as above. However, at the discretion of the treating investigator, such patients may receive an additional treatment of the same termed "**Consolidation**".

Consolidation treatment is identical to Induction. If, after Consolidation treatment, these patients achieve CR or PR, they should proceed to Maintenance (see below for description). If, however, these patients are still SD or have progressed to PD, they should be taken off treatment and treated with R-CHOP or similar chemotherapy at the discretion of the local treating investigator.

Patients achieving **CR** or **PR** after the Induction course may receive an additional treatment of the same termed "**Consolidation**". Consolidation treatment is identical to Induction. For patients achieving CR after Induction, in whom avoidance of maintenance therapy is sought, Consolidation may be given as their final planned therapy. Patients who achieve CR after Induction may proceed directly to Maintenance therapy at the discretion of the treating investigator (for instance, if they are not likely to tolerate Consolidation therapy given the toxicity they experienced during Induction).

Following Consolidation, patients will proceed to **Maintenance:** 1.8 mg/kg IV infusion over 30 minutes once every 3 weeks (1 cycle = 3 weeks), for one year from starting induction or until progression of disease. At the discretion of the treating investigator, patients may discontinue brentuximab vedotin after 10 maintenance doses.

4.1.4 **Dose escalation on a per-patient basis (for both Phase I and Phase II):**

For any patient treated with a brentuximab vedotin dose of 0.8 mg/kg for 2 or more 21-day cycles without DLT, subsequent doses can be increased to 1.2 mg/kg, **but only at the discretion of the treating investigator.** *NOTE: the*

basis for escalation, or lack thereof, should be clearly documented in the Treatment eCRF.

4.1.5 Recommended treatment off study in the event of progressive disease or loss of response:

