1000-1499/ μL	
-1st Occurrence: Withhold current dose until ANC $\geq 1,500/\mu\text{L}$ and platelets $\geq 100,000/\mu\text{L}$. Do not replace missed doses. Restart next treatment at previous dose.
 
-2nd Occurrence: Withhold current dose until ANC $\geq 1,500/\mu\text{L}$ and platelets $\geq 100,000/\mu\text{L}$. Do not replace missed doses. Restart next treatment at 50% previous dose.
 
-3rd Occurrence: Withhold current dose until ANC $\geq 1,500/\mu\text{L}$ and platelets $\geq 100,000/\mu\text{L}$. Do not replace missed doses. Restart next treatment at 25% previous dose.
 
-4th Occurrence: Discontinue protocol therapy.

500-999/ μL	
-1st Occurrence: Notify treating investigator. Withhold current dose until ANC $\geq 1,500/\mu\text{L}$ and platelets $\geq 100,000/\mu\text{L}$. Do not replace missed doses. Restart next treatment at 50% previous dose.
 
-2nd Occurrence: Withhold current dose until ANC $\geq 1,500/\mu\text{L}$ and platelets $\geq 100,000/\mu\text{L}$. Do not replace missed doses. Restart next treatment at 25% previous dose.
 
-3rd Occurrence: Discontinue protocol therapy.

<500/ μL	
-1st Occurrence: Withhold current dose until ANC $\geq 1,500/\mu\text{L}$ and platelets $\geq 100,000/\mu\text{L}$. Restart next treatment at 25% previous dose.
 
-2nd Occurrence: Discontinue protocol therapy.

*G-CSF (Filgrastim), including Neulasta®, may be added for low ANC while a dose reduction is instituted at treating physician's discretions.

TABLE 3b: Drug-Related Hematological Toxicity Dose Reductions for Brentuximab vedotin - Platelets

Platelets	Action
100,000/ μL	None.
75,000-99,000/ μL	
-1st Occurrence: Withhold current dose until ANC $\geq 1,500/\mu\text{L}$ and platelets $\geq 100,000/\mu\text{L}$. Do not replace missed doses. Restart next treatment at previous dose.
 
-2nd Occurrence: Withhold current dose until ANC $\geq 1,500/\mu\text{L}$ and platelets $\geq 100,000/\mu\text{L}$. Do not replace missed doses. Restart next treatment at 50% previous dose.
 
-3rd Occurrence: Withhold current dose until ANC $\geq 1,500/\mu\text{L}$ and platelets $\geq 100,000/\mu\text{L}$. Do not replace missed doses. Restart next treatment at 25% previous dose.
 
-4th Occurrence: Discontinue protocol therapy.

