- Asymptomatic elevated amylase and lipase (for patients with amylase elevation $>3x$ upper limit of normal, but no abdominal pain):
 - Grade 1 – continue at same dose level
 - Grade 2 – continue at same dose level
 - Grade 3 – withhold treatment until toxicity resolves to \leq Grade 2 and then resume treatment at the same dose level. Missed doses will not be made up.
 - Grade 4 – withhold treatment until toxicity resolves to \leq Grade 2 and then resume treatment at reduced dose level or discontinue at the discretion of the treating investigator
- Mild to moderate pancreatitis (hyperamylasemia syndrome – characterized by abdominal pain of <72 hours duration with amylase and/or lipase elevation): Withhold brentuximab vedotin. May consider resuming, with 1 dose level reduction, when signs, symptoms and laboratory values (i.e., amylase and lipase) return to baseline/normalize. If a 2nd episode of mild to moderate pancreatitis occurs, brentuximab vedotin must be permanently discontinued. Missed doses will not be made up.
- Severe pancreatitis (abdominal pain of 72 hours and amylase elevation of 3x normal for > 72 hours duration): Permanently discontinue brentuximab vedotin.

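### The neuropathy rule restarts brentuximab vedotin at a fixed 1.2 mg/kg with no cap at the current dose, so as written it raises the dose of a patient already reduced below 1.2 mg/kg

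*Combined protocol and SAP*

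**What the plan says.** Under the management of peripheral neuropathy in section 4.3, after new or worsening Grade 2 or 3 neuropathy "brentuximab vedotin should be withheld until neuropathy improves to Grade 1 or baseline and then restarted at a dose of 1.2 mg/kg". Missed doses are not made up, and Grade 4 neuropathy ends brentuximab vedotin.

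Footnote 1 to Table 4 leaves this bullet as the only dose rule for neuropathy: "This table should be followed for all non-hematological toxicities EXCEPT peripheral neuropathy" (it also excepts hyperamylasemia and pancreatitis).

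The other brentuximab restart rules in section 4.3 are relative to the dose the patient was on:
- Tables 3a and 3b (ANC, platelets) restart at the previous dose, or at 50% or 25% of it, for example "Restart next treatment at 50% previous dose".
- Table 4 (Grade 3-4 non-hematological toxicity) says to skip until recovery, "then reduce by 33" percent.
- For Grade 3 asymptomatic amylase elevation: "resume treatment at the same dose level".
- For mild to moderate pancreatitis: "May consider resuming, with 1 dose level reduction".

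Two passages deal with raising a reduced dose. The opening text of section 4.3 says that "the dose may be restarted or increased for that individual patient in the event that the toxicity resolves completely", at the treating investigator's discretion. Section 4.1.4, headed for both phases, says that for a patient treated at "0.8 mg/kg for 2 or more 21-day cycles without DLT, subsequent doses can be increased to 1.2 mg/kg", again only at the investigator's discretion.

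**The concern.** A dose-modification rule triggered by toxicity should lower the dose or leave it unchanged. This one sets a fixed number, so its direction depends on where the patient starts. It is the only brentuximab restart rule in section 4.3 given as an absolute dose. The relative rules listed above cannot raise a dose; this one can.

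It also conflicts with section 4.1.4. There, going from 0.8 to 1.2 mg/kg requires at least two 21-day cycles without DLT and a decision by the investigator. The neuropathy bullet takes the same step straight after Grade 2-3 neuropathy, with neither condition.

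At stake is a patient whose dose was cut for, say, neutropenia and who then develops neuropathy. A site following the text would give that patient more drug on restart than before the neuropathy. The statistical design is not involved.

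**Working it through.** The plan gives no figure to reproduce here; the check is direct arithmetic on the dosing rules.

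**Inputs**
- Weekly dose in Induction and Consolidation: 1.2 mg/kg; Maintenance dose: 1.8 mg/kg (section 4.1.1.1).
- Hematological reductions: 50% or 25% of the previous dose (Tables 3a and 3b). A first ANC below 500/µL, or first platelets below 50,000/µL, goes directly to 25%.
- Non-hematological Grade 3-4 reduction: 33% per episode, for up to two episodes (Table 4).
- Restart dose after Grade 2-3 neuropathy: 1.2 mg/kg.

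**Formula.** Change on restart = 1.2 / current dose − 1.

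| Route to the current dose | Current dose (mg/kg) | 1.2 / current | Change as written | Restart with cap, min(1.2, current) |
|---|---|---|---|---|
| Maintenance, full | 1.8 | 0.67 | −33% | 1.2 |
| Maintenance, one Table 4 cut | 1.8 × 0.67 = 1.21 | 0.99 | about 0 | 1.2 |
| Maintenance, two Table 4 cuts | 1.8 × 0.67 × 0.67 = 0.81 | 1.49 | +49% | 0.81 |
| Maintenance, 50% | 0.90 | 1.33 | +33% | 0.90 |
| Maintenance, 25% | 0.45 | 2.67 | +167% | 0.45 |
| Weekly, full | 1.2 | 1.00 | 0 | 1.2 |
| Weekly, one Table 4 cut | 1.2 × 0.67 = 0.80 | 1.50 | about +50% | 0.80 |
| Weekly, 50% | 0.60 | 2.00 | +100% | 0.60 |
| Weekly, 25% | 0.30 | 4.00 | +300% | 0.30 |

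With the cap, no ratio exceeds 1.00.

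**Sensitivity to wording.** If restarting at 25% of the previous dose was meant as a 25% reduction, the weekly dose becomes 1.2 × 0.75 = 0.9 mg/kg and the restart is still +33%. The conclusion does not depend on that reading. Nor does it need the 0.8 mg/kg Phase I de-escalation level in section 4.1.2; the routes through Tables 3a, 3b and 4 are enough.

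**When the cases can arise.** In the usual order (one full dose, one withheld, one reduced), reaching 0.6 or 0.3 mg/kg uses up the three Induction doses. A neuropathy restart from those levels would therefore fall in optional Consolidation or later. The protocol does not say whether a percentage cut made in Induction carries into Maintenance.

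**The case against.** The strongest case is that section 4.3, read as a whole, does not order an increase.

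- **Most severe toxicity governs.** The opening of section 4.3 says adjustments follow the most severely affected system. An investigator could take this as grounds to keep the lower dose. But it does not say so, and once the earlier toxicity has resolved, neuropathy is the governing system, which leads back to 1.2 mg/kg.
- **Raising a reduced dose is already regulated.** The re-escalation sentence requires complete resolution and is discretionary. That sentence is permissive, however, while the neuropathy bullet is directive and needs only recovery to Grade 1 or baseline. It does not limit the bullet.
- **Loose wording elsewhere.** Table 4's Grade 0-2 row refers to the original starting dose, which read just as literally would also ignore earlier cuts. That is fair as a comment on drafting, but that row is not a restart rule.
- **Section 4.1.4 has narrow scope.** It covers only 0.8 mg/kg and says nothing about 0.9, 0.6, 0.45 or 0.3 mg/kg. This stands: the direct conflict with 4.1.4 is confined to the 0.8 mg/kg case.
- **A sensible investigator would not raise the dose.** Probably true. But section 11.6 requires the study to be run as the protocol describes except in emergencies, so keeping such a patient at 0.6 mg/kg would depart from the written rule.
- **Few patients are exposed.** Section 1.2.1.1 gives dose delays of 14% for neutropenia and 11% for sensory neuropathy on monotherapy. Assuming independence, both occur in 0.14 × 0.11 = 1.5%, or about 0.4 of 24 Phase II patients. Doubling both rates gives 0.28 × 0.22 = 6.2%, or about 1.5 patients. Only one order of events matters, which lowers these figures. Other dose-reducing toxicities and weekly combination dosing could raise them. Section 3.1.6 also admits patients with ANC from 750/mcL and platelets from 50,000/mcL, within the ranges where Tables 3a and 3b act if the low count is drug-related. The number is likely to be small; that limits the impact but does not make the rule right.

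**Conclusion.** The concern holds. As written, the bullet raises the dose by 33% to 300% for patients at the singly reduced levels of 0.9 to 0.3 mg/kg. It makes no reduction for a patient at the full weekly dose, and works as evidently intended only from full-dose Maintenance. This rests on a literal reading of the bullet and on the reductions in Tables 3a, 3b and 4 being applied as stated. It assumes no particular frequency: the documents give none for a dose cut followed by Grade 2-3 neuropathy. It should be fixed as a patient-safety matter, although few patients are likely to be affected and no efficacy analysis changes.

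**What to change.** Reword the bullet in section 4.3 so that, after recovery to Grade 1 or baseline, brentuximab vedotin is *restarted at 1.2 mg/kg or the patient's current dose (the last dose given before withholding), whichever is lower*. This keeps the 1.8 to 1.2 mg/kg step and removes every increase. Any later increase would then come under section 4.1.4, where it applies, or the discretionary re-escalation sentence in section 4.3.

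Whether neuropathy at the full weekly dose of 1.2 mg/kg should also lead to a lower restart level is a clinical decision for the sponsor; no value is proposed here.

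The cost is one reworded bullet in a protocol amendment and a notice to sites. No procedures, patients or analyses are added.
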